9.2 Secondary Endpoints

The secondary endpoints of this study are

- 1) an increase in *ex vivo* phagocytosis of *Escherichia coli* by peripheral white blood cells
- 2) a decrease in white blood cell activation when cells are incubated with an inflammatory stimulus (e.g. Platelet activation factor). This will be achieved by assessing the expression of adhesion molecules on peripheral blood cells using flow cytometry and fluorescently conjugated antibodies.

9.3 Sample Size

Power calculations were conducted using data obtained from published studies where healthy volunteers were given 1 mg essentially (from a different source to that being investigated in the present study) and peripheral blood lipid mediator levels were evaluated pre-essential fatty acid and 4 hours after supplement intake (Colas et al Reference 17). Using pre and post values of 10 mediators values from these studies and Wilcoxon matched-pairs signed rank test a sample size of 33 participants is required to detect a threefold odds of an increase in post value when compared with the pre value with a power of 80% at the 5% level of statistical significance using the formulae from reference 18. Fifty mediators will be examined and it is recognized that at the 5% level of statistical significance around 2-3 mediators will falsely be identified as having significant changes. However the functional effect of all significant mediators will be subsequently examined by assessing white blood cell function, including the ability of peripheral white blood cells to phagocytose bacteria and the response of peripheral white blood cells and platelets to an inflammatory stimulus. If we do not observe increases in the ability of peripheral white blood cells to phagocytose bacteria and/or decreases in the activation of peripheral white blood cells and platelets then these mediators will be assumed to be false positive results. For these analysis the white blood cell function and peripheral blood lipid mediator levels at the 2h and 4h intervals post essential fatty acid/placebo administration will be compared to pre-supplementation values. The time point and dose that give the greatest change in all the mediators and the greatest regulation of peripheral white blood responses will be judged to be the main outcome measure for future trials.

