5.5 Rationale for choice of doses

Given that in a study using a different fish oil source and formulation we found that 1 g of essential fatty acids gave a mild but significant increase in plasma SPM levels (25) we chose the lowest dose in the study to be of 1.5g. We then chose to investigate two other doses that were within the **European Food Safety Authority's Tolerable Upper Intake Level for supplements containing both EPA and DHA (See Appendix 2 and 3)**. Given that this limit is of 5 g and previous study with both healthy volunteers and patients demonstrated that doses up to 4 g are well tolerated (22-24), we chose the remaining 2 doses to be 3.0 g and 4.5 g. In addition, this supplement was awarded a **Generally Recognized as Safe Status (see appendix 1)** in the for a dose of up to 5 g. Similar doses of the emulsion from of the fish oil supplement are also being used in an ongoing clinical study in the USA (ClinicalTrials.gov Identifier: NCT02719665) measuring different outcomes to those being investigated in the present study.

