7.4 Study Design / Plan – Study Visits

This is an open label double-blind, placebo controlled, crossover study that aims to determine the dose of omega-3 fatty acids that leads to an increase in peripheral blood SPM levels and the kinetics of this regulation.

- Each participant will give a baseline blood sample then they will be given one of the randomly allocated three doses of fish oil supplement, or a matching placebo in one of 8 study groups [this will be on a 1:1:1:1:1:1:1:1 ratio]. Blood will be collected again at 2h, 4h, 6h and 24h after supplementation/placebo.

- This design allows to compare the levels of SPM pre and post supplementation and therefore to account for inter participant variation in circulating SPM levels as well as for any differences in white blood cell responses *ex vivo*.

- Using a crossover design and a placebo, diurnal variation in the levels of SPM (currently not known) will be checked. In addition, using each volunteer as their own control for comparison with each dose of supplement will further improve the power of the study.

- Each participant is expected to be involved in the study for a maximum of 11 weeks from initial consent and screening.

- Participants will be asked to refrain from consuming caffeine containing drinks at least 2h prior to their visit.

- Participants will be expected to refrain from alcohol intake for at least 24h before screening for the study, and for at least 24h before each cycle of the study.

- Participants will also be asked not to take other supplements, medications for the duration of the study, and to avoid fish containing meals for 2 days before each study cycle.

- For each cycle, the participants will make two visits, the first visit will be of a maximum of 8hrs. Here baseline (0hrs) blood sample will be obtained and the supplement/placebo given.

- Blood will be collected 2hrs, 4hrs and 6hrs following supplement/placebo intake and the participant will be free to leave after the 6hrs blood collection.

- During this time participants will be asked to refrain from drinking caffeine containing drinks such as coffee or tea.

- Participants will then be asked to return the next day (24h after fish oil supplement/placebo intake).

[figure not shown]
- The 24h blood draw should take a maximum of 30 min.

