9.4 Statistical Analysis Plan

Wilcoxon matched-pairs signed rank test will be used to analyse the pre and post values of 10 mediators as well as white blood cell function (at 2 and 4h). The time point corresponding to the greatest number of the mediators being statistically significantly different from their pre-test values at the 5% level of statistical significance will be identified as the time point of interest. At the 5% level of significance testing 50 mediators will result in at least 2-3 associations being falsely statistically significant. Thus, the functional effect of all significant mediators will be subsequently examined by assessing white blood cell function, including the ability of peripheral white blood cells to phagocytose bacteria and the response of peripheral white blood cells and platelets to an inflammatory stimulus to determine if the identified associations are likely to be true changes. If we do not observe increases in the ability of peripheral white blood cells to phagocytose bacteria and/or decreases in the activation of peripheral white blood cells and platelets then these mediators will be assumed to be false positive results. Values at different times will not be compared just the value at each time point will be compared to the same person's pre test values.

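### The only rule that names a dose ranks observed changes, and no planned analysis compares a dose with placebo or with another dose, so the dose aim in 7.4 has no analysis that answers it

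*Combined protocol and SAP*

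**What the plan says.** Section 7.4 states that the study "aims to determine the dose of omega-3 fatty acids that leads to an increase in peripheral blood SPM levels", together with the kinetics. Each of 40 participants receives 1.5 g, 3.0 g, 4.5 g and placebo in a four-cycle crossover (5.5, 8.3). Section 7.4 gives two reasons for that design: the placebo cycle lets diurnal variation in SPM, described as unknown, be checked, and each volunteer serves as their own control for every dose.

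One sentence in Section 9 names a dose. The end of 9.3 looks for "The time point and dose that give the greatest change in all the mediators and the greatest regulation of peripheral white blood responses", and carries that choice forward as the principal measure for later studies.

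Section 9.4 has a selection rule of its own, but it concerns time only: the time point with the most significant mediators "will be identified as the time point of interest". The test is the Wilcoxon matched-pairs signed rank test of post-dose against pre-dose values, and "just the value at each time point will be compared to the same person's pre test values". Section 9.3 says the same of values "at the 2h and 4h intervals post essential fatty acid/placebo administration will be compared to pre-supplementation values". The synopsis promises to tabulate any relation between dose and the primary variables, and says the data will not be formally analysed.

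**The concern.** Which doses raise SPM is a question about where an effect is present. Which dose shows the greatest change is a question about rank. The plan poses the first in 7.4 and has a rule only for the second.

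The gap matters most if the doses act similarly. Section 5.5 makes that a reasonable case to plan for: it reports that "1 g of essential fatty acids gave a mild but significant increase in plasma SPM levels", and every dose in this trial is larger. Under similar effects, sampling error largely decides which dose comes first. The reader of the results would get a named dose with no test, interval or margin to show how easily another could have been named, and 9.3 carries that choice into future trials.

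The pre/post tests do not close the gap. Section 9.4 does not say how results at three doses become a statement about dose. A rise from baseline at 2 h or 4 h also mixes the supplement with any time-of-day change. The placebo cycle was included to separate these, but no contrast with it is written.

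**Working it through.** **1. The plan's own figure.** Section 9.3 asks for 33 participants to detect threefold odds of an increase, with 80% power at the 5% level. Threefold odds give p = 3/(1+3) = 0.75. Noether's signed-rank formula is n = (z_alpha + z_beta)² / [3(p − 0.5)²].
- One-sided 5%: (1.645 + 0.842)² / (3 × 0.0625) = 32.97, so 33, which reproduces the figure.
- Two-sided 5%: (1.960 + 0.842)² / 0.1875 = 41.9, so 42.

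The plan does not state sidedness. The figure is for one pre/post comparison; it was not derived for comparing or selecting doses.

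**2. Effect size used below.** For a normal within-person change with SD 1, P(increase) = 0.75 corresponds to a mean of 0.674 SD. Assumptions: one SPM summary, n = 40, and zero mean change in the placebo cycle. The correlation rho between a person's changes in different cycles is not in the documents, so it is varied.

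**3. Ranking by greatest change** (simulation, largest median change, rho = 0; share of trials in which each dose ranks first):

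| True effects in SD, lowest / middle / highest dose | Lowest | Middle | Highest |
|---|---|---|---|
| 0.674 / 0.674 / 0.674 | 33% | 33% | 34% |
| 0.60 / 0.65 / 0.674 | 25% | 35% | 40% |
| 0.34 / 0.50 / 0.674 | 7% | 24% | 69% |

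The first row follows from symmetry and holds for any n or rho. In the second row the lowest dose gives 0.60/0.674 = 89% of the top effect. The gap of 0.074 SD is small beside the standard error of a difference between two mean changes, √[2(1 − rho)/40]: 0.224 at rho = 0 and 0.158 at rho = 0.5. The third row shows that a steep response is ranked more reliably.

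**4. What the pre/post tests can do.** At 0.674 SD and n = 40, a two-sided 5% signed-rank test at a single dose has about 98% power, so an increase over baseline at the lowest dose could be shown. Two things are missing: the placebo contrast and a rule across doses. With no effect at any dose, three independent unordered tests give at least one false upward result in 1 − 0.975³ = 7.3% of trials.

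**5. Ordered tests against the placebo cycle.** For each person, D = change on the dose − change on placebo, with SD √[2(1 − rho)]. The standardised effect is 0.674/1.414 = 0.48 at rho = 0 and 0.674/1 = 0.67 at rho = 0.5. Signed-rank tests run from highest to lowest dose at two-sided 5%, stopping at the first that is not a significant increase. The probability that all three doses are shown active, with equal effects and n = 40:

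| rho | 0 | 0.3 | 0.5 | 0.7 |
|---|---|---|---|---|
| Probability | 0.62–0.64 | 0.83 | 0.96 | >0.99 |

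With no effect at any dose, the sequence declares a dose active in about 2.5% of trials. The same sequence against pre-dose values succeeds in about 95% at rho = 0, but it cannot exclude diurnal variation.

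**6. Precision of a dose-to-dose difference.** The approximate 95% half-width is 1.96 × 0.224 = 0.44 SD at rho = 0 and 1.96 × 0.158 = 0.31 SD at rho = 0.5. That is useful as an estimate but too wide to prove that two doses are equal.

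**The case against.** **The aim does not say lowest.** Section 7.4 speaks of the dose that leads to an increase, and no section gives a reason to prefer a lower one. A reader might infer that the trial is meant to find the minimum effective dose and that the 9.3 rule defeats this. The text does not support that. It does not say maximum either, so the mismatch between presence and rank remains.

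**The rule is for planning.** Section 9.3 frames it as a choice for future trials, which is legitimate in a study that the synopsis calls exploratory. This stands, and it is a reason to keep the ranking. It does not supply an analysis for 7.4.

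**A lower dose can be shown to work.** A reader might infer that the plan cannot show that a lower dose suffices. That goes too far: pre/post tests read by dose could show a rise at 1.5 g, and the synopsis allows the dose relation to be described. What is missing is the placebo contrast, a decision rule and an estimate of differences between doses.

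**The plan will not necessarily name a higher dose.** The split of 33% lowest and 67% higher under equal effects is a three-way tie on one SPM summary. The written rule also requires the greatest white-cell regulation. If the two criteria err independently under equal effects, they agree on one dose in 3 × (1/3 × 1/3) = 33% of trials: 11% the lowest, 22% a higher one, and 67% no dose. If the response falls by 10% and 20% at the higher doses, the lowest ranks first on SPM 50% to 59% of the time (n = 33 or 40, rho 0 or 0.5). So no claim that the plan will usually name a higher dose is made here.

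**Similar effects are not the sponsor's stated premise.** By 5.5 and 5.3, the 1 g result came from another oil and formulation and was given with aspirin, which 7.2 bars here. Similar effects are plausible, not established.

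**Conclusion.** The concern holds in this form. The plan has an aim about which dose raises SPM, a rule that ranks doses by observed change, and no comparison of any dose with placebo or with another dose. Followed as written, it yields a dose choice without a measure of uncertainty. If the doses act similarly, that choice is largely noise on an SPM measure: the lowest dose ranks first about 33% of the time with equal effects and about 25% at about 90% of the top effect. These figures assume one SPM summary, 40 participants, normal changes and, for the 25%, zero correlation between cycles. With a steep dose response the ranking would be more reliable, but still reported without an interval.

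This should be changed before analysis, since the crossover already collects the data needed. It takes no view on which dose is right.

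**What to change.** In 9.4, for the SPM measure and time point fixed as primary:

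1. Compare the within-person change on each dose with the same person's change in the placebo cycle. Test in fixed order from highest to lowest, each at two-sided 5%, and stop at the first that is not a significant increase.
2. Report which doses show an increase as the answer to the 7.4 aim.
3. Report within-person differences between adjacent doses with 95% CIs, as estimates. Without a prespecified margin they do not prove a plateau.
4. Keep the greatest-change rule in 9.3 as a descriptive ranking for planning future trials, reported with those CIs.
5. Bring the synopsis statement on formal analysis into line with 9.4.

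The cost is analysis work and wording. No further participants, visits or samples are needed, and the ordered tests need no split of the 5% level. The fix depends on a decision the plan has not yet made: 9.3 and 9.4 mention both 10 and 50 mediators, and 9.4 picks the time point from the results, so a primary measure and time must be fixed first. There are two limits. If the response is not monotone, the sequence can stop early and leave a lower dose untested. If changes are uncorrelated between cycles, the chance of showing all three doses active is only about 0.62 to 0.64 even when all have the assumed effect.

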9.4 Statistical Analysis Plan

Wilcoxon matched-pairs signed rank test will be used to analyse the pre and post values of 10 mediators as well as white blood cell function (at 2 and 4h). The time point corresponding to the greatest number of the mediators being statistically significantly different from their pre-test values at the 5% level of statistical significance will be identified as the time point of interest. At the 5% level of significance testing 50 mediators will result in at least 2-3 associations being falsely statistically significant. Thus, the functional effect of all significant mediators will be subsequently examined by assessing white blood cell function, including the ability of peripheral white blood cells to phagocytose bacteria and the response of peripheral white blood cells and platelets to an inflammatory stimulus to determine if the identified associations are likely to be true changes. If we do not observe increases in the ability of peripheral white blood cells to phagocytose bacteria and/or decreases in the activation of peripheral white blood cells and platelets then these mediators will be assumed to be false positive results. Values at different times will not be compared just the value at each time point will be compared to the same person's pre test values.

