4. SUMMARY/SYNOPSIS

Short Title	SPM regulation by Fish Oil Supplements in Healthy Volunteers
Methodology	A randomised, double-blind, placebo-controlled study to determine whether fish oil supplementation regulates peripheral levels of specialized pro-resolving mediators and white blood cell responses in healthy volunteers
Research Sites	Barts and The London School of Medicine Queen Mary University of London William Harvey Research Institute [name]
Objectives/Aims	The objective of this study is to learn more about the biology of fish oil supplementation in human healthy volunteers by assessing the actions of these supplements in healthy volunteers.
Number of Participants/Patients	40
Main Inclusion Criteria	Able to provide informed consent, willingness to abstain from fish for 2 days before each study visit, physical examination, laboratory tests.
Statistical Methodology and Analysis (if applicable)	The results will be tabulated and assessed for biological activity of the fish oil supplement and any relationship between dose and primary variables. Because the study is exploratory in nature, there will be no formal statistical analysis of the data.
Proposed Start Date	July 2016
Proposed End Date	April 2016
Study Duration	9 months

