6. TRIAL OBJECTIVES

6.1 Aim of research

The aim of this research is to investigate whether fish oil supplementation increases the peripheral blood levels of SPM and whether fish oil supplementation also regulates peripheral white blood cell responses (including neutrophils, monocytes and platelets) to inflammatory stimuli.

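### Sections 9.3 and 9.4 define no dose-versus-placebo comparison, so a time-of-day change in SPM can be read as a supplement effect

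*Combined protocol and SAP*

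**What the plan says.** The aim in section 6.1 is to "investigate whether fish oil supplementation increases the peripheral blood levels of SPM". Under section 8.3 every participant receives all three doses and placebo, in one of eight sequences.

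Section 7.4 gives two reasons for this design. "Using a crossover design and a placebo, diurnal variation in the levels of SPM (currently not known) will be checked", and "using each volunteer as their own control for comparison with each dose of supplement will further improve the power of the study".

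The analysis is in section 9:

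- Section 9.4: "Wilcoxon matched-pairs signed rank test will be used to analyse the pre and post values of 10 mediators", with white-cell function tested the same way at 2h and 4h.
- Section 9.4 on the form of comparison: "Values at different times will not be compared just the value at each time point will be compared to the same" person's pre-test value.
- Section 9.3, which covers the placebo cycle as well: cell function and mediator levels "at the 2h and 4h intervals post essential fatty acid/placebo administration will be compared to pre-supplementation values".
- Section 9.4 on the time point of interest: "The time point corresponding to the greatest number of the mediators being statistically significantly different from their pre-test values" at the 5% level.
- Both sections treat significant mediators as false positives if white-cell function does not also improve. That check is pre/post too.

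Section 9.3 then uses the time point and dose with the greatest change to define the main outcome for future trials.

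**The concern.** A pre/post test within one cycle asks whether levels changed after dosing. It does not ask whether they changed because of the supplement. If SPM levels rise between 0h and 2h or 4h on any day, with or without fish oil, the test can be significant on all three doses. A downward drift could hide a real rise in the same way.

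The placebo cycle is there to separate these explanations, but section 9 gives it only its own pre/post test and no rule for using the result. Reading the two tests side by side does not fill the gap, because a significant result on a dose and a non-significant one on placebo is not a test of the difference between them.

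The primary question and the time point carried into future trials are at stake. Dose ranking is less exposed, since drift shared equally by all cycles cancels when doses are compared at one time point.

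**Working it through.** **Inputs from the documents.** Threefold odds of an increase, 80% power, 5% level and 33 participants (9.3); 40 to be recruited, and the sequence table (8.3).

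**Assumptions.** Two-sided tests and normally distributed changes. Drift of 0.2, 0.3 or 0.5 SD of the within-person change, equal in all cycles, with no supplement effect. Correlation ρ between one person's changes in two cycles of 0 to 0.5. The documents give neither drift nor ρ.

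**1. The plan's own figure.** Threefold odds means P(post > pre) = 3/(1+3) = 0.75. A one-sample proportion formula gives

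n = [(1.96×0.5 + 0.842×√(0.75×0.25)) / 0.25]² = 28.9.

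With continuity correction this is (28.9/4)×[1 + √(1 + 2/(28.9×0.25))]² = 32.8, so 33. The stated size is reproduced for a pre/post test. The formula actually used cannot be confirmed. Under normality, 0.75 corresponds to a shift of 0.674 SD.

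**2. False positives from drift.** Simulated signed-rank tests, 20,000 trials per setting, per mediator, before the white-cell check:

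| Drift (SD) | 0 | 0.2 | 0.3 | 0.5 |
|---|---|---|---|---|
| Pre/post, n=33 | 4.7% | 18.8% | 36.6% | 77.4% |
| Pre/post, n=40 | 5.1% | 22.4% | 44.2% | 85.2% |
| Rise on dose, no significant rise on placebo, n=33, ρ=0 | 2.3% | 15.2% | 23.2% | 17.9% |
| Same, n=40, ρ=0 | 2.5% | 17.4% | 24.6% | 12.5% |

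The placebo-corrected contrast stays at 4.6% to 5.3% throughout, if there is no carryover. Rows 3 and 4 show that informal reading beside placebo does not restore the error rate; at ρ=0.3 they are a few points lower.

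**3. After the white-cell check.** Suppose either of two independent cell outcomes suffices. At n=33 the check passes in 4.9% without cell drift, and in 34.4%, 59.7% and 94.9% if the cell outcomes drift equally in the favourable direction. Multiplying by row 1 (mediators and cell outcomes taken as independent):

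- Cells do not drift: 0.188×0.049 = 0.9%; 0.366×0.049 = 1.8%; 0.774×0.049 = 3.8%.
- Cells drift too: 0.188×0.344 = 6.5%; 0.366×0.597 = 21.9%; 0.774×0.949 = 73.5%.

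**4. Time-point rule.** Ten mediators, 2h against 4h, drift at 4h only:

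- No supplement effect, 0.3 SD drift: 4h is picked in 84% (n=33) or 92% (n=40), against 23% without drift and about 25% on placebo-corrected changes. Most of the rest in those two comparisons are ties.
- True effect of 0.3 SD at 2h only, 0.3 SD drift at 4h: 4h is picked in about 41% to 43%. With independent mediators at n=40 the figure is 41%, against 0.5% without drift and about 4% placebo-corrected.
- Full planned effect (0.674 SD) at 2h, 0.3 SD drift at 4h: 4h is picked in about 0.1%.

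**5. Power of the placebo-corrected contrast.** Its SD is √(2(1−ρ)), so the standardised effect is 0.674/√(2(1−ρ)) = 0.477, 0.570 and 0.674 at ρ = 0, 0.3 and 0.5.

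- Simulated signed-rank power is 73%, 87% and 96% at n=33, and 82%, 93% and 98% at n=40.
- A sign-type formula is less favourable. With p = Φ(0.477), Φ(0.570), Φ(0.674) = 0.683, 0.716, 0.750, scaling gives 33×(0.25/(p−0.5))² = 61.4, 44.3 and 33, so 62, 45 and 33 participants. Power at n=40 is 62%, 76% and 87%.

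**6. Carryover.** In the sequence table placebo follows 4.5 g directly in Groups 2 to 4 and 1.5 g directly in Groups 5 to 7, which is six of eight, with a minimum gap of 48h. If carryover lowered the placebo change by 0.2, 0.3 or 0.5 SD in those six, the placebo-corrected error rate at n=40 and ρ=0 would be about 10%, 16% and 35%.

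**The case against.** - **The white-cell check is the plan's last step, and it may hold.** If only the mediators drift, it brings the error below 5% (step 3). Section 7.4 calls only SPM variation unknown and says nothing about drift in cell function. This stands as a limit on size. But the check is not specific to a mediator, its and/or wording is loose, and it has no placebo comparison, so its protection rests on an untested assumption.
- **A strong real effect would dominate drift.** This stands for the time point: with the full planned effect at 2h, drift at 4h hardly moves the choice. With a weak effect it does.
- **The documents do show an intention to compare.** A pre/post test is a form of own control, the synopsis speaks of relating dose to the primary variables, and no sentence forbids a treatment comparison. No method is attached to any of these.
- **The study is exploratory.** The synopsis says "there will be no formal statistical analysis of the data". Sections 9.3 and 9.4 nevertheless set 5% tests and let them shape future trials.
- **Handling drift is limited.** Section 8.7 requires processing within one hour and uses internal standards, so the point rests on diurnal variation alone.
- **The remedy assumes no carryover.** This stands as a real condition (step 6). That calculation moves only the placebo cycles and in one direction, although many dose cycles also follow active dosing.

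**Conclusion.** The concern holds. No section defines a dose-versus-placebo contrast for any outcome, and the plan followed as written cannot separate a supplement effect from a change over the day. That omission is certain from the text; its size is conditional.

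Under assumed drift of 0.2 to 0.5 SD, the per-mediator error before the white-cell check is about 19% to 77% at n=33 and 22% to 85% at n=40. After the check, at n=33, it is about 1% to 4% if cell outcomes are stable and about 6% to 73% if they drift. The choice of time point is at risk when the true effect is weak or absent, and hardly at risk at the full planned effect. The protocol itself treats diurnal variation as unknown, so it gives no basis for assuming zero drift. The contrast should be specified before treatment codes are broken.

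**What to change.** In sections 9.3 and 9.4:

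1. Make the primary contrast, for each dose and time point, (post minus 0h on the dose) minus (post minus 0h on placebo) within participant. Test it by paired Wilcoxon. Log values would be preferable. A mixed model on change from 0h with treatment, time, their interaction, period, sequence and participant is an alternative.
2. Use the same contrast for the white-cell outcomes, so that the false-positive check is also placebo-corrected.
3. Choose the time point and dose from placebo-corrected changes.
4. Report estimates with 95% confidence intervals, and keep the pre/post tests as descriptive.
5. Compare 0h values across periods and by preceding treatment as a carryover check. This will detect only carryover visible before dosing, so state the remaining assumption.
6. Restate power at 40 for this contrast over a range of between-cycle correlations.

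**Cost.** New wording and a new power statement. No visits or samples are added, since section 8.9 already schedules the placebo-cycle draws. The contrast is noisier: at the planned effect, 40 participants give 82% to 98% signed-rank power, or 62% to 87% by the sign-type formula, before dropout or multiplicity control. If the restated power is too low, either more participants are needed or the lower power must be declared.

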9. STATISTICAL CONSIDERATIONS

9.1 Primary Endpoint

The Primary endpoint of the study will be an increase in peripheral blood SPM levels that will be measured using established liquid chromatography tandem mass spectrometry based approach.

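### The kinetics aim has no time-course estimate: 9.4 picks a time by counting significant tests, 9.3 picks it by another rule, and the role of the 6h sample is unsettled

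*Combined protocol and SAP*

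**What the plan says.** All references are to the combined protocol and SAP.

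- **Aim and sampling (7.4).** The study is to determine "the dose of omega-3 fatty acids that leads to an increase in peripheral blood SPM levels and the kinetics of this regulation". Blood is drawn at baseline and at 2, 4, 6 and 24h in each of four cycles. The same section says the placebo and crossover serve to check diurnal variation in SPM, which it describes as unknown at present.
- **Endpoint (9.1).** "The Primary endpoint of the study will be an increase in peripheral blood SPM levels". No time is named.
- **Tests (9.4).** Wilcoxon signed-rank tests will "analyse the pre and post values of 10 mediators as well as white blood cell function (at 2 and 4h"). The section also refers to 50 mediators: "At the 5% level of significance testing 50 mediators will result in at least 2-3 associations being falsely statistically significant". Its last sentence reads in part "Values at different times will not be compared just the value at each time point will be compared", the comparison being with that person's own baseline.
- **Selection rule in 9.4.** The time of interest is "The time point corresponding to the greatest number of the mediators being statistically significantly different from their pre-test values" at the 5% level.
- **Selection rule in 9.3.** "The time point and dose that give the greatest change in all the mediators and the greatest regulation of peripheral white blood responses" will set the main outcome measure for future trials.
- **Times in 9.3.** White-cell function and "peripheral blood lipid mediator levels at the 2h and 4h intervals post essential fatty acid/placebo administration will be compared to pre-supplementation values".
- **Missing samples (8.11).** A missing 0, 2, 4 or 6h sample takes the participant out of the primary analysis; a missing 24h sample does not. The main analysis is per-protocol on complete cycles, with a secondary intention-to-treat analysis of all data.
- **Synopsis (4).** Results will be tabulated. The study is called exploratory, with no formal statistical analysis.

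**The concern.** To describe kinetics one must estimate how large the change is at each time and how long it lasts. The plan contains no profile, area under the curve, peak, time to peak, repeated-measures or time-by-dose analysis. The step closest to a time-course conclusion is the count in 9.4. It records how many mediators cross a significance threshold, not by how much they move, and it is taken on change from baseline without subtracting the change on placebo. As worded it also takes any difference, although the endpoint is a rise.

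The selected time is meant to be used: 9.3 says the chosen time and dose will define the outcome measure for later trials. If 9.3 and 9.4 name different times, nothing in the plan says which one stands. A reader also cannot tell whether a peak at 6h or persistence to 24h would be tested or only tabulated.

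**Working it through.** **1. The plan's own sample size.** From 9.3: threefold odds of an increase, 80% power, 5% level, N = 33.
- Probability of an increase: p = 3/(1+3) = 0.75.
- Noether signed-rank formula: N = (z_α + z_β)² / [3(p − 0.5)²], with denominator 3 × 0.0625 = 0.1875.
- One-sided 5%: (1.645 + 0.842)² = 6.183 from unrounded values; 6.183/0.1875 = 32.97, so 33.
- Two-sided 5%: (1.960 + 0.842)² = 7.849; 7.849/0.1875 = 41.86, so 42.
- Two-sided sign-type formula: [1.960 × 0.5 + 0.842 × √(0.75 × 0.25)]² / 0.25² = 28.9, or 32.8 with a continuity correction, so again 33.

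The stated figure is therefore reproducible, but from either a one-sided or a two-sided calculation, so it does not settle sidedness. It covers one paired comparison, not a time course.

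**2. Which times count.**
- 7.4 draws samples at 2, 4, 6 and 24h.
- 8.11 treats 6h as required and 24h as optional for the primary analysis.
- 9.3 names 2h and 4h for mediators and white-cell function, but the sentence may belong only to the functional check that precedes it.
- 9.4 names 2h and 4h in a bracket that may apply only to white-cell function. Its last sentence speaks of each time point, which may mean all four.

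Across three active doses the planned mediator tests could number from 10 × 2 × 3 = 60 to 50 × 4 × 3 = 600. The plan does not say which set the count uses, whether it runs within or across doses, or what happens in a tie.

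**3. What the count responds to.** For one mediator at time t and dose d, the change from baseline on supplement is drift(t) + effect(t, d). On placebo it is drift(t). Subtraction leaves effect(t, d). The count in 9.4 uses the first quantity alone, so time-of-day drift can add to it. Each mediator contributes 0 or 1, so a change just past the threshold counts the same as one several times larger.

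**4. Illustrations under assumed effects.** The documents give no effect sizes by time or correlations, so these show only what the rule can do. Setting: 33 participants, 2,000 simulated trials, normal changes in SD units, correlation 0.5 between two times, and two-sided signed-rank tests by normal approximation.
- *Direction.* 40% of mediators rise by 0.7 SD at 2h and 60% fall by 0.7 SD at 4h. With 10 or 50 mediators and between-mediator correlation from 0 to 0.5, the two-sided count selects 4h, the time of the fall, in 92% to 100% of trials. Counting only significant rises selects 2h in more than 99%.
- *Magnitude.* All 10 mediators rise by 0.6 SD at 2h; 5 of 10 rise by 1.8 SD at 4h and the rest do not change. Mean change is 0.6 SD at 2h and (5 × 1.8)/10 = 0.9 SD at 4h. With between-mediator correlation 0.3, the count selects 2h in about 95% of trials, while reading 9.3 as mean change points to 4h.

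**The case against.** The strongest reply is that this is an exploratory study. Kinetics appears in one design sentence in 7.4 and not in the aim, hypothesis or endpoints of section 6, and the synopsis disclaims formal analysis. That limits how serious the point is. It does not remove it, because 9.4 nevertheless tests at 5% and 9.3 uses the result to fix the outcome measure of future trials.

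Several stronger readings are tempting, and the documents do not support them.
- *The count certainly ignores direction.* Sidedness is never stated, 9.3 powers for an increase, and 33 matches a one-sided calculation. The objection about falls is conditional on two-sided tests.
- *9.4 contradicts itself by barring comparison of times and then choosing one.* Its last sentence can be read as excluding only hypothesis tests between times.
- *Drift would go unseen.* 9.3 applies the pre/post comparison to placebo cycles too, so drift could be noticed. It is still not removed from the count.
- *No magnitude criterion exists.* 9.3 has one. The trouble is that it differs from 9.4 and has no stated precedence.
- *The 6h and 24h samples go unanalysed.* The wording is ambiguous, and 9.4 may cover all four times.
- *The rule often fails to decide.* With no true effect, 10 independent mediators and two independent times, ties occur about 46% of the time, but 0.95^20 = 36% are cases with nothing significant at either time, where naming no time is correct. Nor is it an error to name one of two equally good times.
- *The 6h condition costs many participants.* The documents give no miss rate, allow replacement, and keep all data in the secondary analysis.

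**Conclusion.** The point holds in a limited form. A stated aim has no time-course estimate. The count in 9.4 does not measure the size of the rise, is not placebo-corrected and, if the tests are two-sided, credits decreases. It can also disagree with the rule in 9.3. The 6h requirement in 8.11 does not fit a section 9 that names only 2h and 4h.

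These conclusions rest on the text. The simulated percentages depend on assumed effects and correlations and show what is possible, not what is likely in this trial. The point does not invalidate the paired tests or the sample size of 33. It should be corrected before analysis because, as written, two careful analysts could report different times.

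**What to change.** 1. Reconcile 8.11, 9.3 and 9.4 on which post-dose times enter the primary analysis. Do not exclude a participant from an analysis for a sample that analysis does not use. State the sidedness of the tests.
2. Keep the paired Wilcoxon tests on which 33 is based. Add, as an exploratory analysis, the placebo-corrected change from baseline with confidence intervals at 2, 4, 6 and 24h by dose, from one repeated-measures crossover analysis, for example on the log scale. Amend the last sentence of 9.4 to allow it.
3. Replace the count with one rule used in both 9.3 and 9.4: the largest estimated placebo-corrected increase over a mediator set named in advance. Give white-cell responses a stated role, and note that a selected maximum is optimistic.

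The cost is revised wording, some additional analysis and the model's assumptions. The samples are already scheduled, and because the added analysis is exploratory the sample-size calculation need not change.
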